9.1. Adverse Event Preferred Term and Body/Organ System Summary Tables

Treatment-emergent adverse events are summarized by treatment as defined by the safety analysis set. In addition to being summarized by treatment year, AEs are also summarized overall.

Treatment-emergent adverse events are events that either:

- Have a complete date of onset on or after the date of first dose and not more than 30 days after the date of the last dose of study drug, or
- Have no recorded date of onset with a stop date after the first dose of study drug, or
- Have no recorded date of onset and stop date.

General considerations for TEAE summaries are:

- Multiple events by PT and SOC are counted once only per patient for summaries of TEAE incidence.
- For summaries of TEAE incidence by severity, only the most severe event is counted per patient.
- For summaries of TEAE incidence by relationship, only the most strongly related event is counted per patient.
- A TEAE with a missing resolution date or incomplete date that is not identified as continuing is assumed to be continuing.
- For summaries of the number of TEAEs, all TEAEs are counted.

Off-treatment AEs (OTAEs) are events with a start date more than 30 days after last dose and not considered treatment emergent. Off-treatment AEs will be summarized separately.

Adverse Events are coded using MedDRA. In MedDRA, each verbatim term is mapped to a preferred term and high-level term (HLT), which is then mapped to a SOC.

The investigator grades the severity of the AEs as mild, moderate, or severe as defined in the study protocol. The investigator grades association or relatedness to the study medication according to criteria specified in Section 11.4 of the protocol.

As defined in the protocol, an SAE is an adverse event (occurring at any dose and regardless of causality) that:

- Results in death;
- Is life-threatening;
- Requires inpatient hospitalization or prolongation of existing hospitalization;
- Results in persistent or significant incapacity or substantial disruption of the ability to conduct normal life functions;
- Is a congenital anomaly or birth defect in an offspring of a patient taking study drug;
- Is an important medical event.

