Medical History									
Height e	X	X	X	X	X	X	X	X	X
Weight in Clinic	X	X	X	X	X	X	X	X	X
Weight at Home	-----X-----								
Dispense Weight & Study Drug Diary	X	X	X	X	X	X	X	X	
Collect/Review Weight & Study Drug Diary	X	X	X	X	X	X	X	X	X
ECG				X	X				X
Echocardiogram f									
Vital Sign Measurements	X	X	X	X	X	X	X	X	X
Comprehensive Physical Exam					X				X
Targeted Physical Exam	X	X	X	X		X	X	X	
Pregnancy Test for WOCBP h	X	X	X	X	X	X	X	X	X
Study Drug Administration	-----X-----								
Dispense Study Drug	X	X	X	X	X	X	X	X	
Collect Study Drug	X	X	X	X	X	X	X	X	X
Telephone Contact									
Adverse Event Collection	X	X	X	X	X	X	X	X	X
Kidney Ultrasound j									
Clinical Chemistry (incl. eGFR) k	X	X	X	X	X	X	X	X	X
BNP and NT-proBNP	X	X	X	X	X	X	X	X	X
Hemoglobin A1c	X			X					X
Hematology	X	X	X	X	X	X	X	X	X
Coagulation	X	X	X	X	X	X	X	X	X
Basic Lipid Panel					X				X
Urinalysis and Microscopy	X	X	X	X	X	X	X	X	X
Urine Collection for ACR l	X	X	X	X	X	X	X	X	X
Virus Serology									
PK Samples a	X								X
SARS-CoV-2 Antibody Test					X				
Ambulatory Blood Pressure Monitoring o	X			X				X r	
Tanner Staging q					X				

	Off-Treatment Period 						
	Wk 103	Wk 104 (A)	Wk 104 (B)	Wk 108 (A)	Wk 108 (B)	Wk 112 (A)	Wk 112 (B)
Off-Treatment: Patients who continued study drug through Wk 100 (visits based on date of last dose)	Day 21 – 25 after last dose	Day 28 – 35 after last dose	Day 29 – 36 after last dose	Day 56 – 63 after last dose	Day 57 – 64 after last dose	Day 84 – 91 after last dose	Day 85 – 92 after last dose
Follow-Up: Patients who discontinued study drug prior to Wk 100 (visits based on Day 1 date)	Day 721 – 725	Day 728 – 735	Day 729 – 736	Day 756 – 763	Day 757 – 764	Day 784 – 791	Day 785 – 792
Informed Consent/Assent							
Inclusion/Exclusion							
Demographics & Baseline Disease Characteristics							
Prior and Concomitant Medications	X	X	X				
Medical History							
Height e	X	X	X	X	X	X	X
Weight in Clinic			X		X		
Weight at Home							
Dispense Weight & Study Drug Diary							
Collect/Review Weight & Study Drug Diary							
ECG			X		X		
Echocardiogram f							
Vital Sign Measurements			X		X		
Comprehensive Physical Exam			X		X		
Targeted Physical Exam							
Pregnancy Test for WOCBP h			X		X		
Study Drug Administration							
Dispense Study Drug							
Collect Study Drug							
Telephone Contact							

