**9.10.16. Adverse Event Collection**

Patients will be observed for general appearance, presence of illness or injury, or signs indicative of a concurrent illness as indicated in Table 4. Patients must be instructed to volunteer any information regarding AEs on or after the first dose of study drug, or sites may query the patients with an open question regarding any AEs they may be experiencing (e.g., “How have you been feeling since your last visit?”). Any findings are to be documented. Patients must be asked if they have been hospitalized, had any accidents, used any new medications, or changed

concomitant medication regimens (including prescription drugs, over-the-counter medications, vitamins, herbal products, and minerals). Responses must be documented in the source documents.

AEs should be reported from the time of the first dose until the Week 112 (B) visit as indicated in Table 4.

For patients who discontinue study drug early (prior to Week 100) and continue to be followed in the study, all AEs should be recorded for 12 weeks following the patient's last dose of study drug. Beyond 12 weeks after the patient's last dose, only those AEs that are relevant to the clinical condition including kidney disease, may have an impact on kidney function, or may impact the interpretation of safety or efficacy data must be recorded in the AE log within the EDC. Unscheduled phone visits may be used, as necessary, to ensure accurate collection of AEs of interest.

AEs that are related to study procedures should be recorded in the AE log within the EDC independent of the patient's study drug status or duration since the patient's last dose of study drug.

See Section 11 for more detail regarding adverse events.

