### **11.2. Adverse and Serious Adverse Events**

#### **11.2.1. Definition of Adverse Events**

##### **11.2.1.1. Adverse Event**

An AE is defined as any untoward medical occurrence in a patient regardless of its causal relationship to study drug. An AE can be any unfavorable and unintended sign (including any clinically significant abnormal laboratory test result), symptom, or disease temporally associated with the use of the study drug, whether it is considered to be study-drug related. Included in this definition are any newly occurring events or previous conditions that have increased in severity or frequency since the administration of study drug.

All AEs that are observed or reported by the patient during the study (from administration of the first dose until the Week 112 (B) study visit as indicated in Table 4) must be reported, regardless of their relationship to study drug or their clinical significance.

For patients who discontinue study drug early (prior to Week 100) and continue to be followed in the study, all AEs should be recorded for 12 weeks following the patient's last dose of study drug. Beyond 12 weeks after the patient's last dose, only those AEs that are relevant to the clinical condition including kidney disease, may have an impact on kidney function, or may impact the interpretation of safety or efficacy data must be reported.

AEs that are related to study procedures should be reported independent of the patient's study drug status or duration since the patient's last dose of study drug. SAEs, if considered related to study drug, can be reported at any time during the study duration.

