##### **11.2.1.2. Serious Adverse Event**

An SAE is any AE occurring at any dose and regardless of causality that:

- Results in death;
- Is life-threatening;
- Requires inpatient hospitalization or prolongation of existing hospitalization;
- Results in persistent or significant incapacity or substantial disruption of the ability to conduct normal life functions;
- Is a congenital anomaly or birth defect in an offspring of a patient taking study drug;
- Is an important medical event.

The term "life-threatening" refers to an event in which the patient was at immediate risk of death at the time of the event. It does not refer to an event that hypothetically might have caused death if it were more severe.

Important medical events are those that may not meet any of the criteria defined above; however, they may be considered serious when, based upon appropriate medical judgment, they may jeopardize the patient and may require medical or surgical intervention to prevent one of the other outcomes listed in the SAE definition.

Pregnancy is not considered an AE; however, information will be collected for any pregnancies that occur during the study (from the time of the first dose of study drug until the Week 112 (B) study visit indicated in Table 4, as appropriate). Certain pregnancy outcomes will require submission as an SAE (see Section 9.8).

The investigator is responsible for reporting to Reata or designee all AEs and SAEs that are observed or reported by the patient during the study (from the time of administration of the first dose of study drug until the Week 112 (B) study visit indicated in Table 4), including events resulting from protocol-associated procedures as defined in relevant legislation, and regardless of their relationship to study drug or their clinical significance. For patients who discontinue study drug early, SAEs should be reported through 12 weeks following the date of last dose of study drug. SAEs, if considered related to study drug, should be reported at any time during the study. The Sponsor may request additional information from the investigator to ensure the timely completion of accurate safety reports.

All SAEs reported or observed during the study must be followed to resolution or until the investigator deems the event to be chronic or the patient to be stable. Reata or designee may contact the investigator to obtain additional information on any SAE which has not resolved at the time the patient completes the study.

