6.2. Data Presentation Conventions

Unless otherwise specified, descriptive statistics for continuous variables include the number of patients with data (N), mean, standard deviation (SD), standard error (SE), first quartile (Q1), median, third quartile (Q3), minimum, and maximum. The same number of decimal places as in the observed value are presented when reporting minimum and maximum; 1 more decimal place than in the observed value is presented when reporting mean and quartiles; and 2 more decimal places than in the observed value are presented when reporting SD or SE.

Categorical data are presented using frequency counts and percentages. All percentages are rounded to 1 decimal place, unless otherwise specified. Percentages equal to 100 are presented as 100% and no percentages are presented for zero frequencies. Where individual variable values are missing, summaries of categorical data are based on reduced denominators (i.e., the denominators include only patients with available data), and the number of missing values is presented. For summaries of AEs and concomitant medications, the percentages are based on the total number of patients in each treatment group.

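### The off-treatment adverse event table has no upper time limit and mixes short complete follow-up with long selective follow-up, so arm percentages can differ with no difference in risk

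*SAP*

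**What the plan says.** SAP 9.1 counts an event as treatment-emergent if it starts "not more than 30 days after the date of the last dose of study drug". For later events it says: "Off-treatment AEs (OTAEs) are events with a start date more than 30 days after last dose and not considered treatment emergent". These are to be summarised separately. SAP 9.1.2 gives the number and percentage of patients by treatment. On the denominator, SAP 6.2 says: "For summaries of AEs and concomitant medications, the percentages are based on the total number of patients in each treatment group". No person-time is mentioned.

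Protocol 9.10.16 sets the collection period: "AEs should be reported from the time of the first dose until the Week 112 (B) visit as indicated in Table 4". In protocol Table 4, Week 112 (B) for a completer is "Day 85 – 92 after last dose". For a patient who stopped before Week 100 it is study Day 785 to 792, counted from Day 1.

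For early stoppers who stay in the study, protocol 9.10.16 says "all AEs should be recorded for 12 weeks following" the last dose. Beyond that, protocol 11.2.1.1 keeps "only those AEs that are relevant to the clinical condition including kidney disease, may have an impact on kidney function", or those that may affect interpretation of safety or efficacy. Protocol 11.2.1.2 adds: "For patients who discontinue study drug early, SAEs should be reported through 12 weeks following the date of last dose of study drug". Drug-related SAEs are reported at any time.

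SAP Table 5 places laboratory, vital sign and ECG values after early discontinuation into windows by days since last dose. Adverse events have no such windows.

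**The concern.** One percentage per arm combines two kinds of follow-up. Completers contribute about 8 weeks of complete recording. Early stoppers contribute about 8 weeks of complete recording and then, possibly, many months in which mainly kidney-related events are kept. The mix in each arm depends on how many patients stopped and when. Stopping happens after randomisation and may be affected by treatment.

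Safety and tolerability is a primary objective, and the primary efficacy endpoint is kidney function after withdrawal. Renal events after stopping will therefore be read closely. A difference between arms in this table could reflect longer kidney-selective observation and be mistaken for a withdrawal effect, or a real difference could be hidden.

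**Working it through.** The documents state no length for the off-treatment event interval, so there is no figure of theirs to reproduce.

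**Inputs.** Lower bound of 30 days after last dose (SAP 9.1). Week 112 (B) at 85 to 92 days after last dose for completers and at Day 785 to 792 for early stoppers (protocol Table 4). Full recording for 12 weeks, or 84 days, after last dose (protocol 9.10.16). Months are days divided by 30.4 (SAP 6.5.1).

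**Length of the interval, by design**
- Completer: 85 − 30 = 55 to 92 − 30 = 62 days (7.9 to 8.9 weeks), all fully recorded.
- Early stopper with last dose on Day d: total = (785 to 792) − d − 30. The selective part is (785 to 792) − d − 84.

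| Last dose | Total days (months) | Selective days (months) |
|---|---|---|
| Day 1 | 754–761 (24.8–25.0) | 700–707 (23.0–23.3) |
| Day 84 (Week 12) | 671–678 (22.1–22.3) | 617–624 (20.3–20.5) |
| Day 336 (Week 48) | 419–426 (13.8–14.0) | 365–372 (12.0–12.2) |

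The fully recorded part for an early stopper is days 31 to 84, which is 54 days. That nearly matches the completer's 55 to 62. The imbalance lies entirely beyond day 84 and concerns only the event types still recorded then.

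**Hypothetical size for kidney events.** Assume 10 per 100 patient-years in both arms, all early stops at Week 40 (Day 280), full retention and full capture of kidney events to Day 784.
- Time at risk: completer 58 days (within the 55 to 62 range); early stopper 784 − 280 − 30 = 474 days.
- Risk = 1 − exp(−0.10 × days / 365.25): 1.58% and 12.2%.
- Arm with 35% stopping: 0.65 × 1.58 + 0.35 × 12.2 = 5.3%.
- Arm with 20% stopping: 0.80 × 1.58 + 0.20 × 12.2 = 3.7%.
- The ratio is 1.43 and the gap 1.6 points, with no true difference. At 30% versus 25% stopping the ratio is 1.13 and the gap about 0.5 points.

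**Is the direction fixed?** Assume stopping of 35% versus 15%, the same constant hazard h of any event in both arms (0.001 to 0.006 per day), and last dose on Day 84 or Day 336. A fraction f of event types is still recorded after 12 weeks. Patients who leave the study on stopping contribute no events. Completer risk is 1 − exp(−58h). Risk for a retained early stopper is 1 − exp(−54h − f·h·(792 − d − 84)). Higher-stopping arm minus the other:
- all retained, f = 10% to 30%: +0.6 to +9.4 points;
- 40% retained, f = 10%: −0.2 to −2.5 points;
- f = 0, retention 40% to 100%: −0.1 to −3.7 points.

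The sign is not fixed.

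**With a limit at day 84.** Every patient still followed has 54 fully recorded days. With equal hazards the risk is 1 − exp(−54h): 5.3%, 15.0% and 27.7% at h = 0.001, 0.003 and 0.006, the same in both arms if retention to day 84 is equal.

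**The case against.** A reader might infer that the arm with more early stopping will look worse, or that bardoxolone will show a false renal excess. The documents do not support that. They give no stopping rate by arm, and the range above changes sign. Several provisions also reduce late capture. Protocol 11.2.1.2 limits SAE reporting in early stoppers to 12 weeks unless drug-related. Patients on maintenance dialysis or with a transplant are followed only for vital status and SAEs (9.1.9), and unblinded patients only for vital status (9.6.1). Tolvaptan use warrants leaving the study (9.3.1.2), and reduced follow-up is allowed (8.5.1).

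Nor can one infer frequent permanent stopping from the protocol's safety rules. Those for transaminases (9.1.2), fluid status (9.1.1) and adolescent weight loss (9.1.4) describe temporary stops. The nausea section (9.1.8) mentions de-escalation, and 9.11 asks for efforts to resume. Different stopping by arm is possible but not shown.

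It would also be wrong to say that collection never ends, since Week 112 (B) closes it, or that all of an early stopper's off-treatment time is selective, since days 31 to 84 are complete.

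The realised effect is limited. According to the change log, the rule of 12 full weeks followed by selective recording came with Version 7.0 (25 May 2022). That is 350 days before study drug was stopped on 10 May 2023 and 428 days before the SAP date of 27 July 2023. The 617 selective days of a Week 12 stop could not have accrued under that rule by the SAP date. The stop also made patients then on drug early stoppers in both arms, and the SAP does not say when their event collection ended.

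Finally, safety is descriptive without testing (SAP 9), treatment-emergent tables are unaffected, all events are listed, and SAP 7.1 counts patients in follow-up by visit. All of this stands and lowers the weight of the point. None of it makes the pooled percentage interpretable.

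**Conclusion.** The point holds as a weakness of presentation. Followed as written, SAP 9.1, 9.1.2 and 6.2 put unequal and partly selective follow-up into one percentage per arm. By design the off-treatment interval runs from 55 to 62 days for a completer to about 25 months for the earliest stopper, of which about 23 months are selective. For a Week 12 stop the total is about 22 months.

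The table can therefore show a difference between arms, especially in renal terms, without a difference in risk. The 5.3% versus 3.7% is an illustration that rests on assumed stopping, event rate, retention and capture. It is not an estimate for this trial, and the direction cannot be predicted from the documents. No test or efficacy estimate is affected. It is a cheap improvement worth making before database lock.

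**What to change.** - In SAP 9.1 and 9.1.2, define the main off-treatment table as events starting more than 30 and up to 84 days after last dose.
- Put later events of early stoppers in a separate table, labelled as selectively collected, with patient-years of off-treatment follow-up by arm.
- Footnote both tables with the patients followed only for vital status or SAEs (protocol 9.1.9, 9.6.1). For them, even days 31 to 84 may not be fully recorded.
- State when event collection ended for patients stopped by the May 2023 decision.
- Reconcile protocol 11.2.1.1 with 11.2.1.2 on what is reported beyond 12 weeks, or state in the SAP which rule the data follow. As written, a serious kidney event judged unrelated to drug is kept under one section and falls outside the other.

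The cost is a few lines of SAP text and one table. Late events leave the main table but stay in the separate table and the listings. A completer loses 55 − 54 = 1 to 62 − 54 = 8 days, and events in those days would appear only in the listings unless a row is added for them. The limit does not correct for unequal retention before day 84.
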